### 4.4. Study Intervention

The study intervention will consist of two phases. An “Educational Intervention” will serve as a wash-in period and will take place in the first six weeks of the study; during this period of time clinical staff at all four hospitals will be trained on the proper usage of ReadyCleanse® and will gain experience using it in the clinical setting before data collection begins. The second phase will be a 42,672-catheter day-period, where data on CAUTI incidence will be collected while the ReadyCleanse® cloth and standardized process is in use for catheter care and maintenance. Figure 4.1 depicts the flow of the intervention.

**Figure 4.1**

Wash-in Period	ReadyCleanse® as standard care for all catheter care and maintenance at all four hospitals															
	1.5	2.5	3.5	4.5	5.5	6.5	7.5	8.5	9.5	10.5	11.5	12.5	13.5	14.5	15.5	16.5
Months																
*Study timeline may extend past 17.5 months. Study duration will be determined via completed catheter days (42, 672)																

## 5. STUDY POPULATION

### 5.1. Inclusion Criteria

- Any adult patient who requires an IUC to be placed during admission to one of the four study hospitals.

### 5.2. Exclusion Criteria

- Patients < 18 years old.
- Patients whose entire hospital stay occurs in:
  - Pediatric unit
  - Psychiatric unit
  - Labor & Delivery or Postpartum units

- Emergency Room

### **5.3. Other Considerations**

Given that this intervention will become the new standard-of-care with respect to catheter care and maintenance in the hospital system, as is appropriate given the product's indications for use, we will not be screening participants (other than age), actively recruiting, or obtaining informed consent. All HIPAA rules will be strictly observed at all times in order to minimize any breaches of patient privacy and confidentiality (please see Section 9 for more details).

## **6. STUDY PROCEDURE**

### **6.1. Events Prior to Intervention**

Clinical staff at the sites will receive training by a Medline Industries, Inc. Clinical Research Associate (CRA) and/or Clinical Product Specialist on the use of the ReadyCleanse® cloths and the standardized cleansing procedure prior to the start of ReadyCleanse® cloth use. Medline staff will offer training sessions to NorthShore health care providers who perform IUC routine catheter care (e.g. patient care technicians, staff nurses, etc.) during all shifts at each hospital to ensure effective and consistent use of the product. The training will also be offered to NorthShore Clinical Care Coordinators, Nurse Educators, and Study Research Nurses, along with NorthShore clinical research staff. Nurse Educators will be responsible for training newly hired personnel or any staff that could not attend the training sessions; Nurse Educators should document all training sessions. Training materials will be a combination of a Medline-produced product use video, review of ReadyCleanse® cloth package instructions, and pre-printed handouts. Medline staff members will be available to assist if any questions arise from the healthcare providers during the course of the study. ReadyBath Intelligent Warmers (Appendix 11.1), which are used to keep the ReadyCleanse® cloths warm to enhance patient comfort, will be placed on the floors. Positioning of the ReadyBath Warmers will be jointly determined by Medline and each of the four study hospital IPs in conjunction with the NorthShore research staff; in some instances it may not be possible to place ReadyBath Warmers due to spatial constraints. As the warming of the product is not essential to its efficacy, this is not anticipated to present a problem in interpreting the study results.

### **6.2. Wash-in Period/Educational Intervention**

The first six weeks of the study will be dedicated to ensuring all staff members who perform catheter care and maintenance are adequately trained on the process of using the ReadyCleanse® cloths and to gain experience in using them. Training will take place as described in 6.1. Once trained, staff will begin using ReadyCleanse® cloths and the standardized cleansing process for perineal care. During this period, no data will be collected pertaining to the efficacy of the intervention.

### **6.3. Intervention with ReadyCleanse®**

Following the Educational Intervention, all hospital staff will be sufficiently trained in the use of ReadyCleanse® and the 42,672-catheter day-data collection period will begin. All participants requiring an IUC during their hospital stay will be considered enrolled in the study, and assigned a subject number. A master list linking subject numbers to patient name and medical record number will be maintained in a secure electronic database by the staff at NorthShore University Health System. This database will be maintained at the research site at all times.

During this time, use of ReadyCleanse® cloths and the standardized cleansing procedure will be the standard-of-care for catheter care and maintenance; patients will undergo routine perineal care for a minimum of twice per day and after each incontinent episode. The specific cleansing procedure for ReadyCleanse® is provided in Appendix 11.1.2.

### 6.3.1. Data Collection Procedures

#### 6.3.1.1. Prospective Data Collection

During the data collection period, the Study Coordinator at the university health system will extract the relevant data from all patients who had an IUC during their hospital admission. Data will be extracted from the participant's Electronic Health Record (EHR) in Epic (www.epic.com) and transferred into both an Excel spreadsheet and a paper Case Report Form (CRF) by NorthShore study staff; a sample of the CRF is provided in Appendix 11.5. The following data will be collected for each participant enrolled in the study and entered into his/her CRF:

#### **Demographic and general health information**

- Age
- Gender
- Race
- Hospital within NorthShore system
- Hospital room during stay

#### **Catheter related data**

- Admission date
- Indication for IUC
- Date catheter was placed
- Date catheter was removed
- Number of catheter days
- Development of CAUTI
- Adverse Event or Serious Adverse Event
  - Yes/No
    - If Yes, prompt to complete paper AE/SAE form

### **CAUTI data**

- Additional data will be collected on each participant who develops a CAUTI, including a urine culture. The full list of additional data collected on patients with a CAUTI is available sample CRF found in Appendix 11.5. This additional data collection is part of the standard practice within the NorthShore University Health System for anyone who develops a CAUTI.

#### 6.3.1.1.1. CAUTI Definition

Patients will be deemed to have had a CAUTI using the criteria currently defined by the Centers for Disease Control (CDC), which can be found here: <https://www.cdc.gov/nhsn/pdfs/pscmanual/7pscgaucurrent.pdf>

#### 6.3.1.1.2. Urine culture

Quantitative urine cultures will be obtained from patients with IUC in-situ for at least 5-7 days. Twenty randomly selected IUC specimens will be obtained during the Educational Intervention period and another 20 samples during the study. Urine will be collected by the research coordinator from the IUC and transported to the research microbiology laboratory at NorthShore in a sterile, leak-proof container labeled with patient's study ID number. 1ul and 10ul loops will be used to streak a blood agar plate and MacConkey agar plate. Both plates will be incubated at 35°C in a non-CO2 incubator and inspected for growth of bacteria after 18-24 hours of incubation. Individual bacterial colonies will be identified using Matrix Assisted Laser Desorption/Ionization-Time of Flight (MALDI-TOF) mass spectrometry and quantity of organism calculated. The CRF specific to this portion of the study is provided in Appendix 11.6. Finally, all participants who develop a CAUTI will have a urine culture performed to determine the causative bacteria and susceptibility pattern.

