3. OBJECTIVES AND ENDPOINTS

OBJECTIVES	ENDPOINTS	JUSTIFICATION FOR ENDPOINTS
Primary		
Evaluate if ReadyCleanse® cleansing cloths reduce CAUTI when used to perform catheter care and maintenance.	The primary endpoint will be incidence of CAUTI, measured per 1000 catheter days. The rate during the intervention will be compared to the historical rate for the facilities for the period preceding the intervention.	This endpoint was chosen as it is a direct measure of the objective of the study, using well-accepted criteria.
Secondary		
Evaluate if use of ReadyCleanse® cloths reduces bacteria counts in urine. This may provide a mechanistic account of any reduction in CAUTI.	Number of colony forming units (cfu/ml) of bacteria in urine from a random sub-sample of participants in the intervention, compared to a random sample collected prior to the intervention beginning.	This endpoint is a direct measure the objective, using well-accepted methodology.
Exploratory		
Evaluate the financial impact of using ReadyCleanse® cloths as the standard-of-care for catheter care and maintenance.	Cost savings in dollars through avoided CAUTIs, taking into account the cost of the product over the standard-of-care.	Common measure of financial savings used in Health Economics Outcomes Research
Gain feedback from healthcare professionals on the use of the product.	Healthcare professionals who administer the intervention will be asked to fill out a questionnaire (Appendix 11.2) about their experience with the product. Mean values from a four-choice scale will be computed for descriptive purposes.	Common survey approach to eliciting feedback on preferences.

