## **4. STUDY DESIGN AND INTERVENTION**

### **4.1. Overall Design**

This is an open-label, superiority study intended to determine if IUC care and maintenance with a prepackaged cloth and standardized cleansing process (ReadyCleanse® Meatal and Perineal Cleansing Cloth) can reduce CAUTI relative to standard-of-care. Four northern suburban Chicago acute-care hospitals, all within the same system (NorthShore University Health System), will implement ReadyCleanse® as the standard-of-care for catheter care and maintenance. An initial training period of six weeks will first occur, during which medical staff will be trained on the appropriate use of the product, and have several weeks to become accustomed to it. Following this six-week training period, data will be collected on incidence of CAUTI prospectively for the duration until all expected catheter days (42,672) have been completed. The incidence rate of CAUTI during the intervention period will be compared to the incidence rate for a similar number of catheter days prior to the six-week training period. A significant reduction in CAUTI rate during the intervention period will be taken as evidence of the ReadyCleanse® cloths and standardized cleansing process likely reducing CAUTI. The end of the study will coincide with the 42,672 catheter days, at which point the study should be adequately powered (see Section 8).

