### 8.2.2. Secondary Endpoint

The secondary endpoint will be an analysis of bacteria in the urine, comparing a random sub-sample of the study sample during the intervention to a random sub-sample of participants during the beginning of the Education Intervention. Samples of urine from the Education Intervention and those taken during the intervention will be compared in two ways. The number of individual bacterial species isolated from the cultures will be compared between the two groups, as well as cfu/ml of bacteria present, which will be quantified as follows:

1. No bacterial growth
2. 100-500 cfu/ml
3. 500-10,000 cfu/ml
4. 10,000-50,000 cfu/ml
5. 50,000-100,000 cfu/ml
6.  $\geq 100,000$  cfu/ml

Parametric or non-parametric measures, depending on the normality of the distribution, will be used to compare the two groups' mean values on these two measures, with the hypothesis that use of ReadyCleanse® may reduce the amount of bacteria in the urine, providing a mechanistic account of how it may reduce CAUTI.

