11.6. Case Report Form: Urine Sub-Analysis

R17-019 Case Report Form: Urine Sub-Analysis			Completed by:		
Demographic Information					
1. Participant Number:		2. Age:	3. Sex: Male  Female 		4. Race (may select more than one): Black  White  Asian  Hispanic  Other 
5. Hospital: E:  G:  S:  H: 			6. Room Number:		
Study Data					
7. Bacteria present in sample			 No growth	 10,000-50,000 cfu/ml	
			 100-500 cfu/ml	 50,000-100,000 cfu/ml	
			 500-10,000 cfu/ml	 > 100,000 cfu/ml	
			Organism(s) identified:		

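### The comparator urine specimens for the only secondary endpoint may come from patients already cleaned with the cloths, and the urine form records nothing that would show which

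*Combined protocol and SAP*

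**What the plan says.** The protocol describes the comparator for the urine endpoint in three places.

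- Section 3 has intervention specimens "compared to a random sample collected prior to the intervention beginning".
- Section 6.3.1.1.2 gives the operating instruction: "Twenty randomly selected IUC specimens will be obtained during the Educational Intervention period and another 20 samples during the study". Patients must have had the catheter in place for at least 5-7 days.
- Section 8.2.2 has "a random sub-sample of participants during the beginning of the Education Intervention".

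Cloth use falls inside that same period. Section 4.4 makes the six-week Educational Intervention the first of two phases of the study intervention and says that staff "will gain experience using it in the clinical setting before data collection begins". Section 6.2 says "Once trained, staff will begin using" the cloths, and adds: "During this period, no data will be collected pertaining to the efficacy of the intervention".

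Form 11.6, used for this sub-study, identifies the participant by number, age, sex, race, hospital and room. Its only study-data item is "7. Bacteria present in sample", with a count category and the organisms found. Form 11.5 holds catheter insertion and removal dates, but sections 6.3.1.1 and 9.1.7.1 describe it for prospective subjects and for retrospective CAUTI cases. Its urine-culture date sits in the block completed only for CAUTI.

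**The concern.** The endpoint is meant to offer a mechanistic account of any fall in CAUTI, so the comparator should represent urine under soap-and-water care. A specimen taken during the Educational Intervention may come from a patient whose catheter has already been cared for with the cloths, and no section excludes such a patient. If the cloths lower bacterial counts, those specimens move the comparator towards the intervention group and shrink the difference.

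A null result could then partly reflect when the comparator was sampled. Form 11.6 does not let a reader tell, because it shows neither the date nor the study period of a specimen.

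**Working it through.** **Text side by side.** The windows in 6.3.1.1.2 (any time in the six weeks) and 8.2.2 (the beginning of the six weeks) are nested, so they can be reconciled with each other. Both conflict with section 3 if the Educational Intervention is part of the intervention, as 4.4 says. The conflict softens if the word means only the later phase, which is how 4.1, 6.3 and 8.2.2 use it. Cloth use during sampling remains possible on either reading.

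**Size.** The documents give no effect size, test, sidedness or power for the urine comparison, so there is no stated figure to reproduce. What follows is illustration.

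From the documents: 20 v 20 specimens, a 42-day Educational Intervention, and a catheter in place at least 5-7 days.

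Assumed:
- standardized effect d = 0.8 and a two-sided 5% t-test;
- effect proportional to the share m of catheter time under cloth care;
- specimen day uniform over W days (7 or 42);
- first cloth use on a unit either on day 0 everywhere, or uniform over R days (14 or 42) after a training lag;
- time in place uniform on 5-7 days, with 7-21 days as an alternative because the protocol states a minimum.

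Power uses the noncentral t with 38 degrees of freedom, critical value 2.024 and noncentrality d(1 − m)√(20/2). Unexposed, the noncentrality is 0.8 × 3.162 = 2.53 and power is 69%.

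Share with any cloth care (no lag): W/(2R) if W ≤ R, giving 7/28 = 25%, 7/84 = 8% and 42/84 = 50%. If W > R it is 1 − R/(2W), giving 1 − 14/84 = 83%.

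Share of catheter time: with cloth use everywhere from day 0 and time in place D ≤ W, m = 1 − D/(2W). With D averaging 6, m = 1 − 6/14 = 0.571 for week 1 and 1 − 6/84 = 0.929 for six weeks. The other values of m come from simulation.

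| Sampling | Cloth start | Any cloth care | m | 0.8(1 − m) | Power |
|---|---|---|---|---|---|
| Week 1 | after a 7-day lag | 0% | 0 | 0.800 | 69% |
| Week 1 | 3-day lag, then over 2-6 weeks | 8-3% | 0.018-0.006 | 0.785-0.795 | 68-69% |
| Week 1 | no lag, over 6 weeks | 8% | 0.033 | 0.774 | 67% |
| Week 1 | no lag, over 2 weeks | 25% | 0.097 | 0.722 | 60% |
| Week 1 | everywhere on day 0 | 100% | 0.571 | 0.343 | about 18% |
| Six weeks | no lag, over 6 weeks | 50% | 0.432 | 0.455 | 29% |
| Six weeks | no lag, over 2 weeks | 83% | 0.762 | 0.190 | 9% |
| Six weeks | everywhere on day 0 | 100% | 0.929 | 0.057 | 5% |

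Other six-week cases: a 7-day lag gives 17-42%; time in place of 7-21 days with no lag gives 13-36%; both together, with starts spread over 6 weeks, give 48% (m = 0.228, effect 0.618). That last case lets some units start after the six weeks end, so it is generous.

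The 18% also depends on time in place. With 7-21 days, m = 3.5 × ln(3)/14 = 0.275, the effect is 0.580, and power is 43%.

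**Checks.** Simulating each specimen's own exposure for the four no-lag staggered cases gave 66%, 60%, 27% and 8%, in table order. A different model, in which a fraction of comparators carries the full effect and power is 80% unexposed (d = 0.91), gave 53% with a quarter exposed and 26% with half.

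**The case against.** The strongest reply is that 8.2.2 governs because it is the narrower window, and that early specimens mostly reflect earlier care. Section 6.1 puts training before first use, so a lag of some days is plausible; at 3 days or more with a staggered start, the week-1 loss all but vanishes. This stands as a real possibility, but not as an assurance. The beginning is not defined, 6.3.1.1.2 allows all six weeks, and section 4.1 describes implementation as simultaneous across the hospital system. That sits badly with a staggered start and, without a lag, leads towards the 18% case.

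Several further objections hold:
- Section 6.2's exclusion of efficacy data may refer to CAUTI alone.
- Specimen containers carry a study ID, so dates are probably recoverable through the master list and the electronic record. Section 6.3 describes assigning subject numbers after the Educational Intervention, however, so that route is not spelled out for these patients.
- Even unexposed, 20 v 20 has only 34% power at d = 0.5, so a null result is weak evidence in any case.
- Restricting to unexposed comparators gains almost nothing under early sampling (62% v 60%, or 67% v 67%, at d = 0.8), so an elaborate restricted analysis is not warranted.
- A unit start date can rule exposure out, but it cannot show that a given patient received cloth care.

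A reader might infer that the comparator was in fact contaminated, or that the loss is known to be large. The documents support neither: they give no sampling dates, training lag or roll-out schedule.

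**Conclusion.** The point holds as an inconsistency and a recording gap. Section 3 does not agree with 6.3.1.1.2 and 8.2.2 on a natural reading. Cloth use is planned in the sampling period, no rule keeps exposed patients out of the comparator, and form 11.6 cannot show which specimens were exposed.

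If the cloth works, any exposure biases the secondary comparison towards no difference. How much is undetermined. Against 69% power unexposed, the assumed cases run from no loss to about 18% for week-1 sampling, and from roughly 5% to 48% for sampling over six weeks. It would be wrong to call the loss small on the strength of 8.2.2, and equally wrong to call it large.

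No false benefit arises. A reader might extend the point to the primary endpoint, but that control is drawn "for a similar number of catheter days prior to the six-week training period" (section 4.1), so it is unaffected. Severity is minor to should-fix. Confidence is high for the inconsistency and low for its size.

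**What to change.** 1. Reconcile sections 3, 6.3.1.1.2 and 8.2.2 to one definition: a comparator specimen is taken before any cloth care of that patient. Count a specimen dated before first cloth use on the unit as unexposed. Clarify in 6.2 whether its statement on data collection covers urine specimens.
2. Add to form 11.6 the specimen date, the study period, and prior cloth care (yes, no or unknown, or the unit's first cloth-use date). Add the catheter insertion date for Educational Intervention patients, whom form 11.5 does not clearly cover.
3. If that period is already over, as the study extension in 6.3.2 suggests, retrieve these items from the electronic record and the training records that section 6.1 asks for. Do so before the urine results are compared; otherwise label the work post hoc.
4. Report how many comparator specimens had prior or unknown cloth care, with a sensitivity comparison in the unexposed if enough remain.
5. If most were exposed, or exposure cannot be established, describe the comparison as early wash-in versus later use and do not draw the before/after mechanistic conclusion.

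The cost is protocol wording, a few fields on a one-page form and a short look-up for up to 40 specimens, with no new cultures. The downside is possibly fewer usable comparator specimens.

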#### 6.3.1.1.3. HCP Feedback

Information pertaining to HCP acceptance of the product will be collected online in Survey Monkey; a link to the survey will be provided via e-mail. Appendix 11.2 provides the form that will be entered into Survey Monkey for HCPs to complete. This will take place approximately in Month 3 of the study. All participating HCPs will be sent an email (Appendix 11.7) asking them to fill out an anonymous survey. The survey will be used to gain feedback from HCPs on the use of the product. It will be stressed that the

survey is anonymous and the HCPs decision whether or not to participate will not affect their current or future status at NorthShore. Only one feedback survey questionnaire will be completed per HCP regardless of the amount of care provided.

#### 6.3.1.2. Retrospective Data Collection

The CAUTI rate during the retrospective portion of the study is already collected; this rate will be compared to the CAUTI rate during the prospective portion of the study. Additionally, the CRF in 11.5 will be completed for any patient who had an IUC and developed a CAUTI in the similar number of catheter days as that of the intervention period, prior to the six-week training period. . These data will be extracted from the participants EHR from the sites electronic data warehouse and entered onto the CRF in the same fashion as the prospective data collection. Data from CRFs for participants in the retrospective arm will be transferred to the same electronic database as the prospective data for statistical analysis.

#### 6.3.2. Compliance with Intervention/Auditing

During the study, random on-site observations of perineal care will be performed by research study coordinators. The study coordinators will directly observe the performance of perineal care for 10 IUC patients at each hospital and adherence to the written protocol will be determined. For sites that have adherence rates below the 90th percentile, we will acquire an additional 10 more observations to reduce the effect of sampling error. Observations of perineal care will be performed during the first seven months of the data collection portion of the intervention, with a goal that all audits are complete within three months.

Due to extension of the study, the second (and subsequent, if required) set of audits will be executed by Medline Industries, Inc., in corroboration with NorthShore University Health System.

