**DOCUMENT HISTORY**

Version	Date	Description of Change	Brief Rationale
1.0	19-Oct-2017	Initial Release	N/A
2.0	20-Mar-2018	Section 4.1: Grammatical edit	Grammatical edit
		Section 5.2: Add exclusion criteria	Protect vulnerable populations (pediatric, pregnant, and psychiatric patients) and exclude Emergency Room, where catheter care is not routinely performed due to short length-of-stay in unit
		Sections 6.1 & 6.2: Revision to training procedures	Explicitly states who will be trained, who is responsible for any training during study, and what materials and equipment will be provided.
		Section 6.3 & 9.1.3: Clarification on database access	Clarification to indicate the sponsor may need access to the master linking list with participant IDs and names in the event of an Adverse Event or other situation. The database will still be housed at NorthShore.
		Section 6.3.1.1: a) Edits to data collection process, b) variables conducted and c) reference to the Case Report Form that can be found in Appendix 11.2.	A) The use of REDCap for electronic CRF capture is no longer an option. Paper CRFs will be created to comply with regulatory requirements and then transferred to an electronic database. B) Certain variables could not be collected for the retrospective group, so these have been updated as well. C) A copy of the paper CRF is referenced in this section, and can be found in Appendix 11.2.
Section 6.3.1.1.3: Edits to the process for collecting healthcare professional feedback on the product.	Clarifies the process for data collection and stresses that participation is strictly voluntary with no impact on employment. A copy of the email that will be sent to potential participants is provided in Appendix 11.7.		

		Section 6.3.1.2: Edit to retrospective data collection process.	Indicate that retrospective data will also be collected using the paper Case Report Form.
		Section 6.3.2: Edit to the compliance process	Compliance will be measured via the internal audits rather than a count of all product used.
		Section 8.2.1: edit to statistical analysis plan and methods for primary endpoint	Minor edits to provide more detail and clarity
		Section 8.2.3.1: Edit to analysis plan of healthcare professional feedback	Indicate these data will be analyzed while study is ongoing
		Section 9.1.4: Edits to Personnel	Inclusion of additional staff members

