The choice of using a retrospective control was due to balancing the need for a high volume of catheter days in order to adequately power the study, and conducting the study in a reasonable timeframe (see section 8). During the intervention period, all four hospitals will continue using their baseline CAUTI bundle prevention measures, and no additional new interventions will take place during the study period. Also, given that this study is using the ReadyCleanse® cloths per their intended use and implementing the intervention simultaneously across the entire hospital system, it takes the form of a quality improvement initiative whereby the use of a retrospective control is commonly used. Nonetheless, conclusions drawn from this study will emphasize the intervention as a whole, such as staff training on how to use the cloths, instructions for how often to use the cloth, as well as the properties of the ReadyCleanse® cloths and standardized cleansing process, in order to make the appropriate conclusion given the known limitations of the use of a retrospective control.

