## 9.1.2. Study Discontinuation and Closeout

### 9.1.2.1 Study Discontinuation

This study may be temporarily suspended or prematurely terminated if there is sufficient reasonable cause. Written notification, documenting the reason for study suspension or termination, will be provided by the suspending or terminating party to the PI, sponsor, and IRB. If the study is prematurely terminated or suspended, the Principal Investigator (PI) will promptly inform the Institutional Review Board (IRB) and sponsor and will provide the reason(s) for the termination or suspension.

Circumstances that may warrant termination or suspension include, but are not limited to:

- Determination of unexpected, significant, or unacceptable risk to participants as determined by Adverse Event review
- Insufficient compliance to protocol requirements
- Data that are not sufficiently complete and/or evaluable

The study may resume once concerns about safety, protocol compliance, and data quality are addressed, and satisfy the sponsor and/or IRB.

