9.1.6. Clinical Monitoring

The CRA will confirm that the rights and well-being of subjects are protected, the reported trial data are accurate, complete, and verifiable from source documents, and will confirm the conduct of the trial by the Investigator and site is in compliance with the protocol, GCP, and regulatory requirements as well as any applicable institution or IRB and federal or local processes. Monitoring will occur at minimum every two months during the study duration or more frequently if:

- The volume or quality of data is large or there is a backlog of review due to unexpected issues
  - This would also include any large volume of CRFs to be reviewed
- The site compliance with the protocol or compliance with expected ICH/GCP and regulatory requirements is lacking or there are continuing unresolved compliance issues
- There are unexpected AE/SAE or subject safety concerns noted
- There are any unexpected inconsistencies with study product management

- There is a request for more frequent monitoring by the site
- Any mutually agreeable situation as determined by NorthShore and Medline

The frequency of routine monitoring may be increased to a longer interval after three monitoring cycles if on-site situations support this change. CRA will discuss this with Medline Associate Director or Clinical Manager and will inform the PI prior to implementation.

Monitoring activities will include subject eligibility, source data review, CRF completion verification, product accountability, site continued suitability, PI study oversight, compliance, etc. and all general monitoring activities as outlined in FDAs Code of Federal Regulations and ICH/GCP guidelines that guide that activity.

Medline may, on occasion, contract with external CROs to provide CRA services and those CRAs are authorized to act on behalf of Medline.

It is expected that the site will be compliant with any institutional SOPs during the execution of the protocol and evidence of that compliance should be readily documented and verifiable by the CRA.

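### Does the one-sided top-up rule for adherence audits in section 6.3.2, with its undefined percentile trigger, need to be changed?

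*Combined protocol and SAP*

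**What the plan says.** Under section 6.3.2, study coordinators will "directly observe the performance of perineal care for 10 IUC patients at each hospital" and judge adherence to the written procedure. The follow-up rule joins a trigger and an action: "For sites that have adherence rates below the 90th percentile, we will acquire an additional 10 more observations to reduce the effect of sampling error." The section does not define how an observation is scored, what distribution the percentile refers to, or how the second set of observations is combined with the first. It assigns later audit sets to the sponsor, working with the health system.

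Four other places bear on how much this matters:

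- The document history for version 2.0 explains the choice of measure: "Compliance will be measured via the internal audits rather than a count of all product used."
- Section 4.1 says that "conclusions drawn from this study will emphasize the intervention as a whole, such as staff training on how to use the cloths".
- Section 9.1.2.1 lists "Insufficient compliance to protocol requirements" among the grounds for suspension or termination, with no numerical limit.
- Section 9.1.6 provides a separate check: "Monitoring activities will include subject eligibility, source data review, CRF completion verification, product accountability, site continued suitability, PI study oversight, compliance".

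Section 8 contains no analysis of adherence.

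**The concern.** There are two apparent faults. First, the trigger as worded is a rank. Taken literally across four hospitals, it flags every hospital below the best one, however good its care. The sponsor may simply have meant 90% adherence, but the text does not say so, and the two readings lead to different numbers of repeat audits.

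Second, the rule is one-sided. A hospital with a chance-low first sample is observed again and its figure moves back towards the truth. A hospital with a chance-high 9 or 10 out of 10 keeps it. If the two sets are pooled, reported adherence is biased upward.

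The audit is the trial's direct observation of whether the cleansing procedure was carried out. With a retrospective control, readers will want to know that. A flattering adherence figure could overstate how fully the intervention was delivered, or soften a judgement that compliance was insufficient.

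**Working it through.** The plan states no adherence rate and no basis for the audit sample size, so there is no figure of its own to reproduce.

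**Inputs.** From the documents: 4 hospitals (section 1), 10 first observations per hospital, and 10 more where triggered (section 6.3.2). Assumed: yes/no scoring, independent observations, the same true rate p in both sets, the trigger read as below 90% (8 or fewer of 10), and pooling within hospital.

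**Bias of a hospital's reported rate.** Let X1 be the number adherent in the first 10. If X1 ≥ 9 the estimate is X1/10; otherwise it is (X1 + X2)/20. Given X1, the expected error is X1/10 − p without a top-up and half of that with one. Since X1/10 is unbiased overall,

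bias = 0.5 × E[(X1/10 − p) × 1(X1 ≥ 9)].

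- p = 0.80: P(9) = 0.2684 and P(10) = 0.1074, so 0.5 × (0.10 × 0.2684 + 0.20 × 0.1074) = 0.0242, or 2.4 points.
- p = 0.90: 0.5 × (0 + 0.10 × 0.3487) = 0.0174, or 1.7 points.
- p = 0.95: 0.5 × (−0.05 × 0.3151 + 0.05 × 0.5987) = 0.0071, or 0.7 points.

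The same formula gives 0.22 points at 50%, a maximum of 2.44 near 82%, and 0.15 at 98%. If the trigger is read as a rank among the four hospitals, the average is 2.4 points at 50%, 2.0 at 80% and about 1.4 at 95%.

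**How many hospitals are flagged.** At a true 80% everywhere, about 2.5 of 4 under either reading. At 95%, 1.5 under the rank reading and 0.34 under the below-90% reading.

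**Total error.** Exact root mean squared error (RMSE) in points. For the first 10 alone it is √(p(1 − p)/10), and for a fixed 20 it is √(p(1 − p)/20).

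| True rate | Pooled top-up | First 10 only | Fixed 20 |
|---|---|---|---|
| 80% | 10.8 | 12.6 | 8.9 |
| 90% | 7.4 | 9.5 | 6.7 |
| 95% | 5.5 | 6.9 | 4.9 |

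The pooled top-up has lower RMSE than the first 10 alone at every rate checked from 50% to 99%.

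**Classification.** A hospital truly at 80% is reported at 90% or more with probability 0.2684 + 0.1074 = 0.376 on the first 10. Pooling adds the case of 8 followed by 10, 0.3020 × 0.1074 = 0.032, giving 0.408. A fixed 20 gives 0.206. A hospital truly at 95% is reported below 90% with probability 8.6%, 4.2% and 7.6% respectively.

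**One overall rate weighted by observations (below-90% reading).** With equal hospitals the bias is at most about +0.6 points. With true rates of 95/95/90/70% it is −2.1, because low hospitals are counted twice; with 95/90/85/80% it is −0.3.

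**The case for a change.** The strongest case for a change is that the rule falls short of its own stated purpose. The extra observations are meant to reduce sampling error, yet they leave a hospital truly at 80% slightly more likely to be reported at 90% or above (40.8% against 37.6%), while 20 observations everywhere would nearly halve that chance. An undefined trigger and an unstated combination rule also leave choices open until results are known, and the sponsor is to carry out the later audits. Stating a percentage and a combination rule would take two sentences.

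The textual points stand, and so does the arithmetic under its assumptions. They do not add up to a needed change, for three reasons.

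- **The size and direction depend on choices the plan does not make.** No hospital-level adherence estimate is planned. An overall rate can be biased the other way. Scoring by step is also plausible, since the procedure in section 11.1.2 has five steps for each sex. With 50 step scores per hospital, treated as independent (a favourable assumption), the bias falls to 0.27 points at 80%, 0.83 at 90% and 0.15 at 95%.
- **The cheap remedy loses accuracy.** Using only the first 10 removes the bias but raises total error, and roughly doubles the chance that a hospital truly at 95% is reported below 90% (8.6% against 4.2%).
- **The better remedy costs fieldwork.** Twenty observations at each of four hospitals is 80. Under the below-90% reading the current rule expects about 40 + 10 × 2.5 = 65 at a true 80% and 40 + 10 × 0.34 ≈ 43 at 95%.

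**Conclusion.** No change to the plan is called for. Section 6.3.2 uses a rank where a percentage was probably meant and leaves the combination of observations unstated. Those reporting the audit can settle both sensibly by giving each hospital's counts and denominators, first set and combined.

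The one-sided top-up does bias a pooled hospital rate upward, by at most 2.4 points and by less than 1 point at 95% or higher. This rests on the below-90% reading, yes/no scoring, pooling within hospital and an unchanged true rate between the two sets. At its largest the bias is about one-fifth of the standard error of 10 observations (2.4/12.6 at 80%), and under pooling the rule does lower total error, as intended. The remaining choice is between a little bias, more variance and more fieldwork, which is a fair trade-off.

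Adherence is neither an endpoint nor a covariate. The Poisson comparison of CAUTI rates in section 8.2.1 does not use it, the compliance ground in section 9.1.2.1 has no threshold that 2 points could cross, and section 9.1.6 monitors compliance separately. No trial result or conclusion turns on this rule.
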